8. STUDY DESIGN

8.1 Design methods

This study is performed in three steps: first, the low dose group (5×10^{10} vp); then, the middle dose group (1×10^{11} vp); at last, the high dose group (1.5×10^{11} vp), with 36 participants in each group. The trial will be carried out step by step from the low dose group to the high dose group, and the participants will be recruited sequentially. The safety data will be evaluated every day, during the study, if any safety problems of the vaccine is noted, recruiting process should be stopped.

8.2 Study endpoints

8.2.1 Primary endpoints

- Occurrence of adverse reactions within 7 days after vaccination.

8.2.2 Secondary endpoint

8.2.2.1 Safety:

- Occurrence of adverse events (AE) within 28 days after vaccination.
- Occurrence of serious adverse events (SAE) within 28 days after vaccination.
- Occurrence of serious adverse events during the whole follow-up period (6 months).
- Changes of safety laboratory measures (hemoglobin, white blood cell count, total lymphocyte count, platelets, creatinine, alanine transaminase, neutrophil, glutamic oxaloacetic transaminase, total bilirubin, and fasting blood glucose) on day 7.

8.2.2.2 Humoral immunogenicity:

- Geometric mean titer of antigen-specific antibody on day 14, day 28, month 3, and month 6 measured by ELISA.
- Seroconversion rate of antigen-specific antibody on day 14, day 28, month 3, and month 6 measured by ELISA.
- Geometric mean fold increase of antigen-specific antibody on day 14, day 28, month 3, and month 6 measured by ELISA.
- Geometric mean titer of neutralizing antibody against SARS-CoV-2 on day 14, day 28, and month 6.
- Seroconversion rate of neutralizing antibody against SARS-CoV-2 on day 14, day 28, and month 6.
- Geometric mean fold increase of neutralizing antibody against SARS-CoV-2 on day 14, day 28, and month 6.
- Geometric mean titer of neutralizing antibody against Ad5 on day 14, day 28, month 3, and month 6.
- Geometric mean fold increase of neutralizing antibody against Ad5 on day 14, day 28, month 3, and month 6.

For uncertain values: when calculating GMT, GMI and seroconversion of antibodies, if the antibody level is below the initial detection limit, half of the initial value will be used; if the antibody level is greater than the detection limit, the maximum dilution will be used.

8.2.2.3 Cellular immunogenicity:

Cell-mediated responses on day 14, day 28, and month 6:

- Positive rate and level of IFN- γ measured by ELISpot.
- Intracellular cytokine staining (ICS) assay to measure positive rates and levels of IFN- γ , TNF α and IL-2 expressed by the active CD4+T and CD8+T lymphocyte.

8.2.3 Exploratory research endpoint

- The correlation between antigen-specific antibody measured by ELISA and neutralizing antibody against SARS-CoV-2.

- The dose-response relationship of antigen-specific antibody measured by ELISA across the dose groups.
- The persistence of the antigen-specific antibody measured by ELISA at month 6.
- The correlation between the initial time of the antibody response and the dose groups.
- The correlation between cell-mediated responses (ELISpot IFN- γ , ICS positive rates of IFN- γ , TNF α and IL-2 expressed by the active CD4+T and CD8+T lymphocyte) and the dose groups.
- The persistence of the cell-mediated responses (ELISpot IFN- γ , ICS positive rates of IFN- γ , TNF α and IL-2 expressed by the active CD4+T and CD8+T lymphocyte) at month 6.
- The correlation between the initial time of the cell-mediated responses (ELISpot IFN- γ , ICS positive rates of IFN- γ , TNF α and IL-2 expressed by the active CD4+T and CD8+T lymphocyte) and the dose groups.

8.3 Study Procedures

From beginning to the end of the study, each participant will complete 9 visits. The visit time, window period and the procedures at the visit are shown in the table 8-3-1-1 and 8-3-1-2.

Table.8-3-1-1 Visit schedule for the participants

Visit No.	V0	V1	V2	V3	V4	V5	V6	V7	V8
Day/month	Day-7 to -1	Day 0	Day 3	Day 7	Day 10	Day 14	Day 28	Month 3	Month 6
Visit interval	Day-7 to -1	Day 0	V1+3 days	V1+7days	V1+10 days	V1+14 days	V1+28 days	V6+2 months	V6+5 months
Time window	--	--	(±1 day)	(±1 day)	(±1 day)	(±2 day)	(±3 day)	(±5 day)	(±15 day)
Recruiting, informed consent	•	•							
Demographic information collection	•	•							
Medical history collection and preliminary screening	•								
Physical examination: Height, weight, blood pressure)	•								
HCG test (for women only)		•							
Blood routine	•			•					
Blood biochemical test		•		•					
HIV antibody test	•								•
Nucleic acid test (pharyngeal swab/sputum)	•								
Nucleic acid test (anal swab)	•								
Axillary temperature measurement	•	•							
Inclusion and exclusion screening	•	•							
Allocation of vaccine ID		•							
Record on the Visit Record Form	•	•							

Blood collection (humoral immunity)	•	•				•	•	•	•
Blood collection (cell immunity)		•				•	•		•
Vaccination		•							
Observation for 6 hours post-vaccination		•							
Safety visit (AR / AE)		•	•	•	•	•	•	•	•
Report serious adverse event (SAE)		•	•	•	•	•	•	•	•
Distribution of diary card (within 14 days)		•							
Return of diary card (within 14 days) and distribute a new diary card (after 14 days)						•			
Return of diary card (after 14 days)							•		
Record vaccination and visits		•	•	•	•	•	•	•	•
Recording of combined medications / combined vaccines		•	•	•	•	•	•	•	•

Table.8-3-1-2 Blood collection at scheduled visits

Visit No.	V0	V1	V2	V3	V4	V5	V6	V7	V8
Visit time	Day-7 to -1	Day 0	Day 3	Day 7	Day 10	Day 14	Day 28	Month 3	Month 6
Visit interval	Day-7 to -1	Day 0	V1+3 days	V1+7days	V1+10 days	V1+14 days	V1+28 days	V6+2 months	V6+5 months

Time window	--	--	(±1 day)	(±1 day)	(±1 day)	(±2 day)	(±3 day)	(±5 day)	(±15 day)
Blood routine (anticoagulant blood)	2ml	--	--	2ml	--	--	--	--	--
Blood biochemistry and HCG (procoagulant blood)	--	3ml	--	3ml	--	--	--	--	--
HIV test (procoagulant blood)	3ml	--	--	--	--	--	--	--	3ml
Humoral immunity (procoagulant blood)	5ml	10ml	--	--	--	10ml	10ml	10ml	10ml
Cellular immunity (EDTA anticoagulant blood)	--	20ml	--	--	--	20ml	20ml	--	20ml
Total blood collection	10ml	33ml	--	5ml	--	30ml	30ml	10ml	33ml

Total amount of blood collection: 151ml.

8.4 Sample size

According to the "Technical guidelines for Vaccine Clinical Trials" issued by the China FDA, the sample size of each vaccine dose group is about 20-30 participants. In this study, 36 participants will be involved in the low-dose group, the middle-dose group and the high-dose group, respectively. A total of 108 participants will be recruited.

8.5 Criteria for pausing or early termination

The investigators will collect daily reports of adverse events after vaccination and report the newly added adverse events to the Data Safety Monitoring Board (DSMB) in time. The DSMB independently analyzes the post-vaccination safety data in each dose group. If an increased risk of participants is found in the course of the study, they send notice to the principal investigator and the sponsor immediately to suspend or terminate the recruiting of participants in clinical trial, during the dose-escalating procedure. If there is a violation of the protocol, GCP or ethical requirements, the sponsor, principal investigator, ethics committee or administrative department shall have the right to suspend or terminate the study, and shall notify other parties and participants and explain the reasons.

Administration of study injections and new enrollments will be paused, if:

- One or more \geq grade 4 adverse reaction or serious adverse event may be associated with vaccination, or
- Occurrence of grade 3 adverse events associated with vaccination in 15% of participants or more (including injection-site reaction, systemic reaction, and change of the safety laboratory measures), or

- Required by sponsor, or
- Required by regulatory authority, or
- Required by institutional review board (IRB).

The study may come to an early termination, if DSMB, sponsor and investigator agree that the risk increased and the risk-benefit for participants is no longer reasonable.

8.6 Duration of study

It will take about 6 months for each participant from recruiting to completing the last visit. Some participants may withdraw during the course of the study.

9 PARTICIPANTS

9.1 Participants selection

Healthy people aged from 18 to 60 years were selected as the target population, and informed in writing by informed consent approved by the ethics committee. On the premise that the volunteers themselves signed the informed consent, they could only participate in the study after passing the physical examination and the following inclusion and exclusion criteria. The investigator conducting the study, the relevant researchers, and any employee of the contract research organization (CRO) shall not be a participant.

9.2 Inclusion criteria

- Aged between 18 and 60 years.
- Able to understand the content of informed consent and willing to sign the informed consent.
- Able and willing to complete all the secluded study process during the whole study

follow-up period (about 6 months).

- Negative in HIV diagnostic blood test.
- Axillary temperature $\leq 37.0^{\circ}\text{C}$.
- Negative serum IgM and IgG to the SARS-CoV-2.
- Chest CT scan is normal (no COVID-19 imaging).
- Pharyngeal swabs or sputum and anal swabs are negative for SARS-CoV-2.
- A body mass index (BMI) are between 18.5 and 30.0.
- Indexes of blood routine, biochemistry and other laboratory tests are within the normal ranges, or not clinical significant judged by doctors (including white blood cell count, lymphocyte count, neutrophils, platelets, hemoglobin, ALT, AST, total bilirubin, fasting blood glucose, creatinine).
- General good health as established by medical history and physical examination.

9.3 Exclusion criteria

- Family history of seizure, epilepsy, brain or mental disease
- Participant that has an allergic history to any ingredient of vaccines
- Woman who is pregnant, breast-feeding or positive in pregnancy test on day of enrollment, or is planning to be pregnant during the next 6 months
- Any acute fever disease or infections
- Have a medical history of SARS infection
- Have serious cardiovascular diseases, such as arrhythmia, conduction block, myocardial infarction, severe hypertension and not well-controlled
- Major chronic illness, such as asthma, diabetes, or thyroid disease, and not well-

controlled

- Hereditary angioneurotic edema or acquired angioneurotic edema
- Urticaria in last one year
- Asplenia or functional asplenia
- Platelet disorder or other bleeding disorder may cause injection contraindication
- Faint at the sight of blood or needles.
- Prior administration of immunodepressant or corticosteroids, antianaphylaxis treatment, cytotoxic treatment in last 6 months
- Prior administration of blood products in last 4 months
- Prior administration of other research medicines in last 1 month
- Prior administration of attenuated vaccine in last 1 month
- Prior administration of subunit vaccine or inactivated vaccine in last 14 days
- Being treated for tuberculosis
- Any condition that in the opinion of the investigators may interfere with the evaluation of study objectives.

9.4 Withdraw from the study

Participants have the right to withdraw from the study at any time during the study period, and the investigator should record the reason of withdraw:

- Participants become pregnant.
- Loss of contact.
- Request to withdraw without any reason.
- Withdraw for reasons unrelated to the study, such as long-term departure,

relocation, etc., and the specific reason for withdrawal should be recorded.

- Withdrawal for reasons related to the study, such as intolerance of adverse reactions, intolerance of biological specimen collection, etc., and the specific reason for withdrawal should be recorded. If a participant withdraw because of AE or SAE, investigator should follow up the participant until the resolve of AE or SAE.
- Participants can require a complete withdraw from the study, all study behaviors could be stopped, including vaccination, biological specimen collection and safety observation. The data before withdrawal will not be used for analysis if he or she require so. If the participants allow the investigators use the data collected before the withdrawal, the data can be included in analysis.
- If a participant is infected by SARS-CoV-2 between day 0 and day 28 post-vaccination, immunogenicity data from he or she will not be included in analysis, but all SARS-CoV-2 infections occurred within 6 months after the vaccination should be documented and reported following the same procedure of SAE reporting, especial attention should be paid in case of the occurrence of antibody-dependent enhancement (ADE).
- Participants can require a partially withdraw from the study, such as refuse to vaccination or blood drawn only, but still participate in other procedures during the follow-up.

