10.7.3 Analyzed data sets selection

Data set for safety evaluation

All participants who received vaccination should be included in the safety evaluation.

Data that violate the scheme should not be excluded.

Data set for immunogenicity evaluation

Full analysis set (FAS) for immunogenicity analysis: FAS is based on ITT (intention to treat analysis) principle to determine the participants. All of the participants that meet the inclusion / exclusion criteria, receiving vaccination, and have at least one blood testing result after vaccination, were included in the FAS set for immunogenicity.

Per-protocol set (PPS): It is a subset of FAS. The participants in the data set were more compliant to the scheme, with no significant deviation or violation of protocol, all met the selection/exclusion criteria and completed vaccination within the vaccination time window according to the requirements of the scheme, and the participants who collected blood at day 0, day 7, day14, day 28 day, month 3 and month 6 month were included in the PPS set. This method of analysis does not include participants who violate the protocol, and confirmed as COVID-19 cases within 14 days after vaccination.

In this study, the FAS are the primary analysis set for immunogenicity evaluation, but the PPS will also be analyzed at the same time. Any difference of analysis results existed between PPS and FAS, will be discussed in the report.

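### Section 9.4 lets a vaccinated participant who withdraws completely have earlier safety data left out of analysis on request, which contradicts the all-vaccinated safety set in 10.7.3, and the protocol does not say which rule prevails

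*Protocol*

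**What the plan says.** Protocol 9.4 allows a complete withdrawal in which study activities can stop, "including vaccination, biological specimen collection and safety observation". It then adds: "The data before withdrawal will not be used for analysis if he or she require so". The sentence after that lets earlier data into the analysis where the participant permits it. Neither sentence separates safety data from immunogenicity data.

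The same section lists, among the expected reasons to withdraw: "Withdrawal for reasons related to the study, such as intolerance of adverse reactions, intolerance of biological specimen collection, etc". For withdrawals caused by an adverse event it also requires: "If a participant withdraw because of AE or SAE, investigator should follow up the participant until the resolve of AE or SAE".

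Protocol 10.7.3 defines the safety data set: "All participants who received vaccination should be included in the safety evaluation", followed by "Data that violate the scheme should not be excluded". The primary endpoint in 8.2.1 is "Occurrence of adverse reactions within 7 days after vaccination", in three uncontrolled dose groups of 36.

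**The concern.** The vaccine is given once, on day 0, so anyone who withdraws after dosing has already been fully exposed. Participants live in designated lodging for 14 days and a doctor visits them daily (10.4.1), so an early reaction will usually be on record before any request is made. Under 9.4 as written, a request then takes out both the recorded event and the exposed person. Under 10.7.3 both stay. The protocol does not rank the two rules.

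This differs from ordinary missing data in two ways. The data were collected and are then set aside, and the participant's experience of the vaccine may be what prompts it. At stake are the analysed 7-day reaction rate, the SAE counts and the comparison between dose groups, in a dose-escalation trial whose primary objective is safety and tolerability.

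**Working it through.** **1. The rules side by side.** Take a participant vaccinated on day 0 who has a recorded reaction on day 2, withdraws completely on day 4 and asks for removal.

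- Section 9.4: the day 0–4 data are not used for analysis.
- Section 10.7.3: the participant is in the safety evaluation.
- Section 9.6.2: participants with protocol deviations stay in the safety analysis. This agrees with 10.7.3 but does not address removal requests.
- Section 9.4, follow-up to resolution, and section 10.4.5, SAE reporting within 24 hours: these govern care and reporting. Neither says the data stay in the analysis.

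The wording of 9.4 shows that a limit could have been written. Its rule on SARS-CoV-2 infection by day 28 restricts the exclusion to immunogenicity data; the removal rule has no such restriction.

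**2. Inputs.** Group size n = 36 (8.4). The plan's total reproduces: 3 × 36 = 108 ("A total of 108 participants will be recruited"). The protocol gives no withdrawal or removal rate, so the number removed, k, is an assumption. For the level of a common reaction, the protocol's summary of the phase II trial of the Ebola vaccine on the same vector platform (4.3.3) gives about 50–65% with at least one adverse reaction within 7 days.

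**3. Formula.** If k participants with the event are removed, x/n becomes (x − k)/(n − k). Intervals are Clopper-Pearson 95%.

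| Situation | All kept | One reactor removed |
|---|---|---|
| Common reaction, x = 18 | 18/36 = 50.0% | 17/35 = 48.6% |
| Common reaction, x = 23 | 23/36 = 63.9% | 22/35 = 62.9% |
| Single severe event, x = 1 | 1/36 = 2.8% (0.1–14.5%) | 0/35 = 0% (0–10.0%) |

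**4. Direction.** For one removal from 36, a removed reactor changes the rate by (x − 1)/35 − x/36 = (x − 36)/1260, which is negative unless everyone reacted. A removed non-reactor changes it by x/35 − x/36 = x/1260, which is positive if anyone reacted. At x = 18 these are −1.4 and +1.4 percentage points (17/35 = 48.6%; 18/35 = 51.4%). The sign of any bias therefore depends on who makes the request.

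**5. The 15% pause level, for illustration only.** Since 0.15 × 36 = 5.4, six participants are needed in a full group. One reactor removed from six gives 6/36 = 16.7% to 5/35 = 14.3%, which crosses the line. One removed from seven gives 7/36 = 19.4% to 6/35 = 17.1%, which does not.

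**The case against.** The strongest reply is that 10.7.3 already contains the right rule for safety, and that 9.4 merely honours a participant's wish in what may be a rare case. Removal needs two acts: complete withdrawal and then an explicit request. Section 9.4 links intolerance to withdrawing, not to asking for removal, and it also lists relocation, dislike of blood sampling and no stated reason. A downward bias is therefore plausible but not shown. On the primary endpoint, any reaction within 7 days, one removal moves the rate by little more than one percentage point at the levels reported for the related vaccine. All of this stands, and it limits the size of the point.

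A reader might infer that removals could pull a group below the 15% grade 3 pause level, or hide a grade 4 reaction or related SAE from the pause rule. The documents do not support that. Section 9.4 speaks of use in analysis, not of reporting. Adverse events go to the safety board daily according to the summary, or promptly according to 8.5, and SAEs are reported within 24 hours. An event would normally be reported before a request, and nothing says the pause count would be recalculated on a smaller denominator.

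It is also fair that following an adverse event to resolution can coexist with leaving its data out of analysis, so that sentence is not part of the contradiction. The conflict is between the removal sentence in 9.4 and the safety set in 10.7.3. A statistical analysis plan that is not shown may define the data sets further, but it should not have to choose between the protocol's safety set and an option that the protocol grants to participants.

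**Conclusion.** The contradiction is real and lies in the current text. For a vaccinated participant who withdraws completely and asks for removal, 9.4 and 10.7.3 give opposite instructions. If 9.4 is followed, observed reactions can leave the safety analysis together with the exposed person, and this could depend on the outcome.

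The effect is small for common reactions but can be decisive for a rare severe one: a single event in 36 becomes none in 35, and the upper 95% limit falls from 14.5% to 10.0%. These figures assume one removal, of a participant who had the event. The frequency and direction of actual requests are unknown, and no effect on the pause rule is established. The point merits correction because the trial's primary purpose is safety and the remedy is simple. It is not evidence that the reaction rates will be materially understated.

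**What to change.** Amend 9.4 to agree with 10.7.3:

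- Withdrawal stops further collection only, with the existing follow-up requirement for adverse events left as it is.
- Safety data recorded up to withdrawal, including adverse events and SAEs that led to it or were open at that time, stay in the safety set.
- Removal on request applies only to immunogenicity data and samples.
- The three dose-specific consent forms are matched to this wording.

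The removal option is a commitment to participants, and the consent forms are not at hand, so a fallback is needed. If the ethics committee or the consent terms require a full removal right, 10.7.3 should state it as an exception. The report should then give the number of requests by dose group and, where permitted, whether a reaction had been recorded. A sensitivity analysis should keep these participants in the denominator and count them as having had a reaction. In the single-event example this restores 1/36 = 2.8%. Where the person removed had no reaction it overstates the rate: with 18 reactors among the remaining 35 it gives 19/36 = 52.8% against a true 18/36 = 50.0%. It therefore serves as a worst case.

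The cost is a short amendment to 9.4, matching consent wording with ethics review, and a somewhat narrower removal option for participants. No new visits or data are needed.

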- The dose-response relationship of antigen-specific antibody measured by ELISA across the dose groups.
- The persistence of the antigen-specific antibody measured by ELISA at month 6.
- The correlation between the initial time of the antibody response and the dose groups.
- The correlation between cell-mediated responses (ELISpot IFN- γ , and ICS positive rates of IFN- γ , TNF α and IL-2

	
expressed by the active CD4+T and CD8+T lymphocyte) and the dose groups.
 
 - The persistence of the cell-mediated responses (ELISpot IFN-γ, and ICS positive rates of IFN-γ, TNFα and IL-2 expressed by the active CD4+T and CD8+T lymphocyte) at month 6. - The correlation between the initial time of the cell-mediated responses (ELISpot IFN-γ, and ICS positive rates of IFN-γ, TNFα and IL-2 expressed by the active CD4+T and CD8+T lymphocyte) and the dose groups.

Scheduled site visits
	
This study has 9 scheduled visits, including V0 (within 7 days before the vaccination), V1 (day 0), V2 (day 3), V3 (day 7), V4 (day 10), V5 (day 14), V6 (day 28), V7 (month 3), V8 (month 6).
 
Chest CT scan and nucleic acid screening before the vaccination:
 
 - All the participants are examined by chest CT, and those with COVID-19 imaging features will be excluded. - Pharyngeal swabs or sputum and anal swabs are collected and detected by RT-PCR or/and NGS methods. Those with positive result will not be involved in the study. 
Humoral immune response:
 
 - V0 (within 7 days before the vaccination): blood will be collected and anti-S and anti-N protein specific IgM and IgG antibodies will be detected by chemiluminescent immunoassay. - V1 (before the first vaccination), V5 (day14), V6 (day 28), V7 (month 3) and V8 (month 6). 10ml of peripheral venous blood will be collected at each visit, and the serum antibodies will be detected by ELISA, neutralization test with SARS-CoV-2 and/or its pseudovirus. 
Cellular immune response:
 
 - V1 (before the vaccination), V5 (day 14), V6 (day 28), V8 (month 6), 20ml of peripheral venous blood will be collected at each visit, and the PBMC will be isolated to detect the level of specific T cell responses.

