10.5.1.3 Evaluation content

The level of specific S protein antibody in serum against SARS-CoV-2 on day 28 post-vaccination will be used as the primary evaluation time point for immunogenicity. The differences of antibody levels among different groups and the changes of antibodies at various time points pre-vaccination and the post-vaccination will be compared.

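### Section 9.4 drops immunogenicity data for SARS-CoV-2 infections on days 0-28, but the set definitions in 10.7.3 exclude only confirmed cases within 14 days (PPS) or state no infection exclusion (FAS)

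*Protocol*

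**What the plan says.** Three places in the current protocol text bear on infected participants.

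- **Section 9.4 (withdrawal):** "If a participant is infected by SARS-CoV-2 between day 0 and day 28 post-vaccination, immunogenicity data from he or she will not be included" in the analysis. No analysis set is named. The same bullet requires that "all SARS-CoV-2 infections occurred within 6 months after the vaccination should be documented and reported following the same procedure of SAE reporting".
- **Section 10.7.3, PPS:** the set leaves out protocol violators and participants "confirmed as COVID-19 cases within 14 days after vaccination".
- **Section 10.7.3, FAS:** participants who meet the eligibility criteria, are vaccinated and "have at least one blood testing result after vaccination, were included in the FAS set for immunogenicity". Infection is not mentioned. The section adds: "In this study, the FAS are the primary analysis set for immunogenicity evaluation".

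Section 10.5.1.3 says that the S-protein antibody level "on day 28 post-vaccination will be used as the primary evaluation time point for immunogenicity". Section 10.5.2.3 gives day 28 the same standing for neutralizing antibody. Under section 10.4.1, participants stay in a designated lodgment for 14 days and go home from day 15.

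**The concern.** The vaccine expresses the S protein, and the immunogenicity readouts are anti-S antibody, SARS-CoV-2 neutralizing antibody and T-cell response. Natural infection can raise the same readouts. Presumably that is why 9.4 removes infected participants up to day 28. If the analysis follows 10.7.3 instead, the protection stops at day 14 in the PPS and is not stated at all in the FAS.

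The unprotected stretch, days 15-28, begins when participants return home and ends at the main antibody sample. The trial has no unvaccinated arm against which an infection effect could be seen. Dose groups are enrolled one after another, so community exposure need not be equal across them. The study is also open-label. If two sections give different answers about who counts, the choice could be made after the titres are known.

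**Working it through.** The protocol states no figure on this point, so there is nothing to reproduce. The check has two parts.

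**1. The rules side by side, by time of infection**

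| Infection | Section 9.4 | PPS, 10.7.3 | FAS (primary), 10.7.3 |
|---|---|---|---|
| Days 0-14 | out | out if a confirmed case | no exclusion stated |
| Days 15-28 | out | not excluded by the infection clause | no exclusion stated |
| After day 28 | documented and reported; no rule for titres | no rule stated | no rule stated |

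Three mismatches follow.

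- *Window.* It is 28 days in 9.4 and 14 days in the PPS.
- *Case definition.* Section 9.4 speaks of being infected; the PPS speaks of confirmed COVID-19 cases. An infection without disease fits the first and perhaps not the second.
- *Scope.* Section 9.4 names no set, and the primary set does not repeat its rule.

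Sections 9.6.1 and 9.6.2 do not list infection as a violation or a deviation, although both lists are open-ended. They do not clearly settle the matter.

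There is also a smaller edge. Table 8-3-1-1 allows the day-28 visit a window of ±3 days, so the sample may be drawn as late as day 31. A rule that ends at calendar day 28 can miss an infection that precedes the sample.

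**2. Size per retained case**

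Inputs:

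- n = 36 per dose group (section 8.4).
- k = 1 infected participant kept in the group.
- F = ratio of that participant's titre to what the vaccine alone would have given. The protocol does not give F; the range 4 to 30 is assumed.

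A GMT is the exponential of a mean of logs, so one value raised F-fold multiplies it by F^(k/n):

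- F = 4: 4^(1/36) = 1.039, about +4%
- F = 10: 10^(1/36) = 1.066, about +7%
- F = 30: 30^(1/36) = 1.099, about +10%

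The geometric mean fold increase moves by the same factor, because the day-0 value is unchanged. The seroconversion rate can move by at most 1/36 = 2.8 percentage points per case.

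For scale, assume a titre SD of 0.4 to 0.6 on the log10 scale (also not in the protocol). The 95% interval for a GMT with n = 36 is then the estimate multiplied and divided by 10^(1.96 × SD/6), that is 10^0.131 = 1.35 to 10^0.196 = 1.57. A one-case shift lies well inside that interval.

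**The case against.** The best defence is that 9.4 is unqualified. It bars these data from analysis without limiting itself to a set, so it can be read as governing FAS and PPS alike. Section 10.7.4 supports this: its exclusions include participants who met withdrawal criteria yet stayed in, and the infection rule is one of the bullets under the withdrawal heading. On that reading a day-20 infection is removed everywhere.

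This has weight. A reader might infer that the protocol contains a third explicit rule keeping infected participants in the FAS. It does not: the FAS definition is silent, and silence can be filled from 9.4. But the defence does not close the point. Section 10.7.3 does not refer to 9.4. The 10.7.4 exclusion names neither infection nor an analysis set, and the infection bullet is a rule about data rather than a plain reason to withdraw. If 9.4 did govern every set, the 14-day PPS clause would be redundant as well as different.

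Three further inferences go beyond the documents.

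- *That the month-3 and month-6 titres, and the month-6 persistence endpoint, are left wrongly unprotected.* The protocol gives no rule for titres after a later infection, but sections 10.7.2 and 10.7.4 refer data sets and methods to analysis plans that are not at hand. That gap alone is not an error. The 14-day against 28-day conflict is different, because the protocol itself fixes both.
- *That discarding an infected participant's earlier samples is a mistake.* It is blunt, but it contradicts nothing.
- *That the trial must add repeated anti-N serology to find silent infections.* That would be a new procedure, not the correction of a misstatement.

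**Conclusion.** The inconsistency is real and stands in the current text. Sections 9.4 and 10.7.3 give different infection windows and different case definitions, and the primary immunogenicity set does not say whether 9.4 applies to it. Followed as written, 10.7.3 would not remove an infection on days 15-28 from the day-28 antibody results.

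The consequence is conditional. An infection has to occur in that window, be retained, and raise the titre. The protocol offers no rate for the first, so the documents do not support saying that the titres are biased upward, only that they could be. The 4% to 10% per case rests on the assumed 4- to 30-fold range.

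The reach is limited too. The primary endpoint, adverse reactions within 7 days, is unaffected; immunogenicity is secondary, and the sample size rests on a guideline rather than on a titre hypothesis. Day 28 is the main time point for antibody. For T cells, sections 10.5.3 and 10.5.4 name day 14 in one place and day 28 in another. This should be fixed, but it does not undermine the trial.

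**What to change.** Reconcile sections 9.4 and 10.7.3 so that both state the same rule, named explicitly for the FAS and the PPS:

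- one infection window, running from day 0 to at least the date of the participant's day-28 sample;
- one case definition, either SARS-CoV-2 infection or confirmed COVID-19 case, used in both places.

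Preferably, word the rule by sample: keep results obtained before the infection date and drop antibody and T-cell results obtained after it. Apply it to the month-3 and month-6 results as well, and report the as-observed analysis, with all results kept, as a sensitivity analysis. The statistical analysis plans should repeat the rule.

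The cost is wording in two sections. No extra visits, samples or assays are needed, because section 9.4 already requires infections to be documented to month 6.
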